10.8.2 HIV Drug-Resistance Analysis

If an HCV/HIV-1 co-infected subject develops a confirmed, plasma HIV-1 RNA level ≥ 500 copies/mL after starting the study, the subject's HIV-1 PR, RT, and/or IN

sequences, as applicable, will be analyzed by Monogram Biosciences using the GenoSure® Prime drug resistance assays. If available and incorporated in the SAS datasets, these results will be presented as data listings.

11.0 Safety Analysis

11.1 General Considerations

Safety data will be summarized using the safety population. Data will be summarized for the overall population.

11.2 Analysis of Adverse Events

Adverse events (AEs) will be coded using the Medical Dictionary for Regulatory Activities (MedDRA). The actual version of the MedDRA coding dictionary will be noted in the clinical study report.

AIDS-Defining Conditions (ADC) will be presented separately (Section 11.3) and will be excluded from all analyses of AEs described below in the rest of Section 11.2.

11.2.1 Treatment-Emergent Adverse Events

Treatment-emergent AEs are defined as any AE with an onset date that is after the first dose of study drug and no more than 30 days after the last dose of study drug. Events where the onset date is the same as the study drug start date are assumed to be treatment-emergent. If an incomplete onset date was collected for an AE, the event will be assumed to be treatment-emergent, unless there is other evidence that confirms that the event was not treatment-emergent (e.g., the event end date was prior to the study drug start date).

11.2.2 Tabulations of Treatment-Emergent Adverse Events

Adverse Event Overview

An overview of AEs will be presented that consists of the number and percentage of subjects experiencing at least one event for each of the following AE categories:

- Any treatment-emergent AE;
- Treatment-emergent AEs with a "reasonable possibility" of being related to ABT-493/ABT-530;
- Treatment-emergent AEs with a "reasonable possibility" of being related to SOF;
- Treatment-emergent AEs with a "reasonable possibility" of being related to RBV;
- Treatment-emergent AEs of Grade 3 or higher;
- Serious treatment-emergent AEs;
- Serious treatment-emergent AEs with a "reasonable possibility" of being related to ABT-493/ABT-530;
- Serious treatment-emergent AEs with a "reasonable possibility" of being related to SOF;
- Serious treatment-emergent AEs with a "reasonable possibility" of being related to RBV;
- Treatment-emergent AEs leading to discontinuation of all study drugs;
- ABT-493/ABT-530-related treatment-emergent AEs leading to discontinuation of all study drugs;
- SOF-related treatment-emergent AEs leading to discontinuation of all study drugs;
- RBV-related treatment-emergent AEs leading to discontinuation of all study drugs;
- Treatment-emergent AEs of Grade 3 or higher with a "reasonable possibility" of being related to ABT-493/ABT-530;
- Treatment-emergent AEs of Grade 3 or higher with a "reasonable possibility" of being related to SOF;
- Treatment-emergent AEs of Grade 3 or higher with a "reasonable possibility" of being related to RBV;
- Serious treatment-emergent AEs leading to discontinuation of all study drugs;
- Treatment-emergent AEs leading to interruption of study drug;

- Treatment-emergent AEs leading to RBV dose modifications (RBV dose increased or reduced);
- Treatment-emergent AEs leading to death;
- Deaths.

Adverse Events by System Organ Class and Preferred Term

The number and percentage of subjects with treatment-emergent AEs will be tabulated by primary MedDRA System Organ Class (SOC) and preferred term (PT) for the summaries listed below. The SOCs will be presented in alphabetical order, and the PTs will be presented in alphabetical order within each SOC.

- Treatment-emergent AEs;
- Treatment-emergent serious AEs;
- Treatment-emergent serious AEs with a "reasonable possibility" of being related to ABT-493/ABT-530;
- Treatment-emergent serious AEs with a "reasonable possibility" of being related to SOF;
- Treatment-emergent serious AEs with a "reasonable possibility" of being related to RBV;
- Treatment-emergent AEs leading to discontinuation of all study drugs;
- ABT-493/ABT-530-related treatment-emergent AEs leading to discontinuation of all study drugs;
- SOF-related treatment-emergent AEs leading to discontinuation of all study drugs;
- RBV-related treatment-emergent AEs leading to discontinuation of all study drugs;
- Treatment-emergent AEs leading to death.

Subjects reporting more than one AE for a given PT will be counted only once for that term (most related incident for the relationship tables). Subjects reporting more than

one AE within an SOC will be counted only once for that SOC. Subjects reporting more than one AE will be counted only once in the overall total.

If a subject has an AE with unknown relationship, then the subject will be counted in the relationship category of "unknown," even if the subject has another occurrence of the same event with a relationship present. The only exception is if the subject has another occurrence of the same AE with a relationship assessment of "reasonable possibility." In this case, the subject will be counted under the "reasonable possibility" category.

A listing of treatment-emergent AEs grouped by SOC and PT with subject numbers will be created for the overall safety population.

Adverse Events by PT

The following summaries of treatment-emergent AEs tabulated according to PT and sorted by the overall frequency across the two treatment arms will be generated:

- Treatment-emergent AEs;
- Treatment-emergent AEs with a "reasonable possibility" of being related to ABT-493/ABT-530;
- Treatment-emergent AEs with a "reasonable possibility" of being related to SOF;
- Treatment-emergent AEs with a "reasonable possibility" of being related to RBV;
- Treatment-emergent AEs of Grade 3 or higher;
- Treatment-emergent AEs of Grade 3 or higher with a "reasonable possibility" of being related to ABT-493/ABT-530;
- Treatment-emergent AEs of Grade 3 or higher with a "reasonable possibility" of being related to SOF;
- Treatment-emergent AEs of Grade 3 or higher with a "reasonable possibility" of being related to RBV.

Subjects reporting more than one AE for a given PT will be counted only once for that term (most severe/highest grade incident for the severity tables and most related incident for the relationship tables). Subjects reporting more than one AE will be counted only once in the overall total.

Adverse Events by Maximum Severity Grade Level

Treatment-emergent AEs will be summarized by maximum severity grade level of each PT tabulated by SOC. Each AE will be assigned a grade level (Grade 1, 2, 3, 4, or 5) by the investigator. If a subject has an AE with unknown severity, then the subject will be counted in the severity grade level category of "unknown," even if the subject has another occurrence of the same event with a severity present. The only exception is if the subject has another occurrence of the same AE with the highest grade level (Grade 5). In this case, the subject will be counted under the "Grade 5" category. The same analyses will be performed for treatment-emergent AEs with a "reasonable possibility" of being related to the study drug, separated by ABT-493/ABT-530, SOF, and RBV.

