6.1.3 Relationship to Study Drug

Assessment of relatedness will be made separately with respect to ABT-493/ABT-530, SOF, and RBV. The investigator will use the following definitions to assess the relationship of the adverse event to the use of study drug:

- Reasonable Possibility** After consideration of factors including timing of the event, biologic plausibility, clinical judgment, and potential alternative causes, there is **sufficient** evidence (information) to suggest a causal relationship.
- No Reasonable Possibility** After consideration of factors including timing of the event, biologic plausibility, clinical judgment, and potential alternative causes, there is **insufficient** evidence (information) to suggest a causal relationship.

For causality assessments, events assessed as having a reasonable possibility of being related to the study drug will be considered "associated." Events assessed as having no reasonable possibility of being related to study drug will be considered "not associated." In addition, when the investigator has not reported causality or deemed it as not assessable, AbbVie will consider the event associated.

If an investigator's opinion of no reasonable possibility of being related to study drug is given, "Other" cause of event must be provided by the investigator for the serious adverse event.

[figure not shown]

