8.1.5.1 Adverse Events

Adverse events will be coded using the Medical Dictionary for Regulatory Activities (MedDRA). The number and percentage of subjects with treatment-emergent adverse events (i.e., any event that begins or worsens in severity after initiation of study drug through 30 days post-study drug dosing) will be tabulated by primary MedDRA System Organ Class (SOC) and preferred term (PT). The tabulation of the number of subjects with treatment-emergent adverse events by severity grade (Grades 1 – 5) and relationship

to each study drug also will be provided. Subjects reporting more than one adverse event for a given MedDRA preferred term will be counted only once for that term using the most severe grade for the severity grade table and the most related for the relationship to study drug tables. Subjects reporting more than one type of event within a SOC will be counted only once for that SOC.

Additional analyses will be described in the statistical analysis plan.

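### Two SAP 11.2.2 counting rules, for adverse events with unknown causality and unknown grade, depart from the protocol without being declared in SAP 12.1

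*SAP*

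**What the plan says.** **Causality.** Protocol 6.1.3 has the investigator assess relatedness separately for ABT-493/ABT-530, SOF and RBV. It equates a reasonable possibility of relationship with the label *associated*, and it covers the missing case: "when the investigator has not reported causality or deemed it as not assessable, AbbVie will consider the event associated". Under its tabulation by system organ class and preferred term, SAP 11.2.2 says instead: "If a subject has an AE with unknown relationship, then the subject will be counted in the relationship category of" *unknown*, even if another occurrence carries an assessment. It then limits this: "The only exception is if the subject has another occurrence of the same AE with a relationship assessment of" *reasonable possibility*, in which case the subject is counted as related. The drug-related rows of the SAP overview, and the drug-related tables, are defined by reasonable possibility or by relation to the named component.

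**Severity.** Protocol 8.1.5.1 counts a subject with repeat events of one preferred term once, "using the most severe grade for the severity grade table and the most related for the relationship to study drug tables". For its tables by preferred term, SAP 11.2.2 adopts the same principle, taking the highest-graded and most related occurrence. Under its maximum-severity tables, however, it says: "If a subject has an AE with unknown severity, then the subject will be counted in the severity grade level category of" *unknown*, even where another occurrence has a grade. One case escapes: "The only exception is if the subject has another occurrence of the same AE with the highest grade level (Grade 5"). The same treatment applies to the maximum-severity tables of events related to each component.

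**Declared changes.** SAP 12.1 lists nine differences between protocol and SAP. Neither counting rule is among them.

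**The concern.** Safety is a primary objective (Protocol 4.0, SAP 4.1), and the adverse event tables are its main output. An event that the protocol calls associated would not be counted as drug-related in the report. A subject with a recorded Grade 4 event and a second, ungraded occurrence of the same term would appear as *unknown* in a table meant to show that subject's worst grade. A missing grade on one occurrence cannot lower a maximum already established by another, so this rule discards information that was collected. The Grade 3 or higher tables in the same report would still count that subject, and a reader would meet two tables that do not agree.

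**Working it through.** The documents give no figure for this point, so there is none to reproduce. The check applies both rule sets to one subject and one preferred term, for each combination of missing and recorded values.

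*Inputs.* Protocol rules: 6.1.3 (missing or non-assessable causality is associated) and 8.1.5.1 (most related and most severe occurrence). SAP rules: 11.2.2, as set out above. Assumption: the SAP's unknown relationship covers what the protocol describes as causality not reported or not assessable.

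*Relationship, for one component:*

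| Occurrences of the same term | SAP | Protocol |
|---|---|---|
| missing only | unknown | related |
| missing + not related | unknown | related |
| missing + related | related | related |
| not related only | not related | not related |

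The rules differ in two of the three patterns that contain a missing value. In the second row, the protocol result takes two steps: 6.1.3 turns the missing assessment into associated, and 8.1.5.1 then takes the most related occurrence.

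*Maximum grade:*

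| Occurrences of the same term | SAP | Protocol |
|---|---|---|
| missing only | unknown | no rule |
| missing + Grade 1 | unknown | 1 |
| missing + Grade 3 | unknown | 3 |
| missing + Grade 4 | unknown | 4 |
| missing + Grade 5 | 5 | 5 |
| Grade 4 only | 4 | 4 |

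Grade 2 follows the pattern of Grades 1, 3 and 4. Where no occurrence is graded, the protocol is silent, so *unknown* contradicts nothing.

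*Reach of each rule.* The relationship rule affects the drug-related summaries. Because relatedness is recorded for three components, one event left unassessed for all of them can affect up to three sets of rows. The severity rule is written only under the maximum-severity heading. The overview counts subjects with at least one event of Grade 3 or higher, and the Grade 3 or higher tables by preferred term take the highest-graded occurrence. A subject with a recorded Grade 3 or 4 event stays in both.

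*Size per subject.* SAP 11.1 pools safety data, and about 50 subjects are planned:

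- 1 subject: 1/50 = 2.0 percentage points
- 2 subjects: 2/50 = 4.0 points
- 3 subjects: 3/50 = 6.0 points

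The range of 1 to 3 is an assumption. An overview row moves only if the subject has no other event that already places him or her in that row.

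**The case against.** The strongest reply comes from Protocol 8.1, which bars imputation in safety analyses and excepts only the SVR endpoints. On a literal reading, an *unknown* category complies with that sentence, and counting missing causality as related does not. It can be added that 6.1.3 sits in the adverse event handling section, that 8.1.5.1 has no rule for missing causality, and that the documents do not say whether 6.1.3 is applied to the data before tabulation. If it is, few or no unknown relationships would reach the tables.

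Part of this stands. The SAP should say how 6.1.3 and 8.1 fit together. But 6.1.3 is a specific classification rule for exactly this case. It is worded for causality assessments in general and is separate from the reporting section, 6.1.5. The SAP does not claim that it is limited to reporting. The no-imputation sentence gives no help to the severity rule, because using a grade that was recorded imputes nothing.

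The practical objection also has weight. Grading and causality are required for every event, and eCRFs are reviewed for completeness, so missing values may be rare or absent. The 2 points are a property of the denominator and are not evidence of an expected effect.

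A reader might also infer more than the documents support:

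- *That Grade 3 and 4 events are lost throughout.* They are displaced only in the maximum-severity tables and their drug-related versions.
- *That missing causality never reaches a drug-related table.* A subject with another related occurrence of the same event is still counted.
- *That the rules act in one direction only.* They cannot raise a related or high-grade count, but they also move subjects out of *not related* and out of Grades 1 and 2. *Unknown* is a category of its own, so these subjects are not dropped from the tables that carry it.
- *That the combination's safety is being described for the first time.* Protocol 3.1 says only that this is the first study of it as a retreatment option, and Protocol 3.2 refers to existing safety data.

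**Conclusion.** The point holds within these limits. The causality rule conflicts with an explicit protocol rule. The severity rule conflicts with the protocol's most-severe-grade rule and with the SAP's own rule for its tables by preferred term, but only in the maximum-severity tables. When triggered, each rule produces a table entry that differs from what the protocol prescribes, and the severity rule can make tables in one report disagree.

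The size is about 2 percentage points per affected subject at N = 50. The number affected is not given and may be zero. The conclusion rests on reading 6.1.3 as governing the tabulations as well as the handling of reports, and on unknown relationship in the SAP meaning unreported or not assessable. The severity part needs neither assumption.

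**What to change.** In SAP 11.2.2:

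1. In the drug-related summaries, classify missing or non-assessable causality as reasonable possibility for the component concerned, citing Protocol 6.1.3. Footnote the number of subjects classified this way. State that this applies the protocol's classification rule and is not imputation of the kind barred by Protocol 8.1.
2. In the maximum-severity tables, including the drug-related versions, use the highest recorded grade for the preferred term. Keep *unknown* only for subjects with no graded occurrence of that term.

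If the sponsor prefers the present rules, both should be listed and justified in SAP 12.1.

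The cost is two sentences of SAP text and a small programming change. Drug-related rates and the graded rows of the maximum-severity tables may be slightly higher.

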11.2.3 Adverse Events of Special Interest

Adverse events of special interest include the following:

- Hepatic decompensation/hepatic failure events, identified using the AbbVie Product MedDRA Query (PMQ) of "Hepatic Decompensation and Hepatic Failure."
- Hepatocellular carcinoma (HCC) events, identified using the MedDRA PTs of hepatocellular carcinoma, hepatic neoplasm, hepatic cancer, hepatic cancer metastatic, and hepatic cancer recurrent.

For the hepatic decompensation/ hepatic failure AE of special interest, the number and percentage of subjects experiencing at least one treatment-emergent AE in the search will be presented by SOC and PT and across all SOCs/PTs. In addition, a by-subject listing of treatment-emergent AEs meeting the search criterion will be provided.

For the hepatocellular carcinoma AE of special interest, a by-subject listing of all post-baseline (i.e., including both treatment-emergent and non-treatment emergent) AEs meeting the search criterion will be provided.

11.2.4 Listing of Adverse Events

The following listings of AEs will be prepared:

- All serious AEs (from the time the subject signed the study-specific informed consent through the end of the study),
- Treatment-emergent serious AEs,
- Treatment-emergent AEs leading to discontinuation of all study drugs,
- Treatment-emergent AEs leading to interruption of study drug,
- Treatment-emergent AEs leading to RBV dose modification,
- Treatment-emergent AEs leading to death.

11.3 AIDS Defining Conditions

A by-subject listing of reported AIDS-Defining Conditions (ADCs), as specified in the protocol, will be provided.

11.4 Analysis of Laboratory Data

Data collected from the central and local laboratories, including additional laboratory testing due to a serious AE, will be used in all analyses.

11.4.1 Variables and Criteria Defining Abnormality

Hematology variables to be summarized include: hematocrit, hemoglobin, red blood cell (RBC) count, white blood cell (WBC) count, neutrophils, bands, lymphocytes, monocytes, basophils, eosinophils, platelet count, reticulocyte count, prothrombin time (PT), international normalized ratio (INR), and activated partial thromboplastin time (aPTT).

Chemistry variables to be summarized include: blood urea nitrogen (BUN), creatinine, total bilirubin, direct and indirect bilirubin, alanine aminotransferase (ALT), aspartate aminotransferase (AST), alkaline phosphatase, sodium, potassium, calcium, inorganic phosphorus, cholesterol, total protein, glucose, triglycerides, albumin, chloride, bicarbonate, magnesium, total insulin, gamma-glutamyl transferase (GGT), creatinine clearance (calculated using Cockcroft-Gault formula), and eGFR (calculated using MDRD equation).

Urinalysis variables to be summarized include: specific gravity and pH.

The definitions of toxicity grades for laboratory parameters are presented in [Table 11](#).

Table 11. Definitions of Toxicity Grades 1, 2, 3, and 4 for Laboratory Values

Test	Grade 1	Grade 2	Grade 3	Grade 4
ALT	> ULN – 3 × ULN	> 3 – 5 × ULN	> 5 – 20 × ULN	> 20 × ULN
AST	> ULN – 3 × ULN	> 3 – 5 × ULN	> 5 – 20 × ULN	> 20 × ULN
Alkaline Phosphatase	> ULN – 2.5 × ULN	> 2.5 – 5 × ULN	> 5 – 20 × ULN	> 20 × ULN
GGT	> ULN – 2.5 × ULN	> 2.5 – 5 × ULN	> 5 – 20 × ULN	> 20 × ULN
Total Bilirubin	> ULN – 1.5 × ULN	> 1.5 – 3 × ULN	> 3 – 10 × ULN	> 10 × ULN
Hemoglobin	< LLN – 100 g/L	< 100 – 80 g/L	< 80 g/L	--
White blood cells	< LLN – 3.0 × 10 ⁹ /L	< 3.0 – 2.0 × 10 ⁹ /L	< 2.0 – 1.0 × 10 ⁹ /L	< 1.0 × 10 ⁹ /L
Absolute Neutrophil Count	< LLN – 1.5 × 10 ⁹ /L	< 1.5 – 1.0 × 10 ⁹ /L	< 1.0 – 0.5 × 10 ⁹ /L	< 0.5 × 10 ⁹ /L
Platelet count	< LLN – 75.0 × 10 ⁹ /L	< 75.0 – 50.0 × 10 ⁹ /L	< 50.0 – 25.0 × 10 ⁹ /L	< 25.0 × 10 ⁹ /L
INR	> 1 – 1.5 × ULN	> 1.5 – 2.5 × ULN	> 2.5 × ULN	--
Glucose (increased)	> ULN – 8.9 mmol/L	> 8.9 – 13.9 mmol/L	> 13.9 – 27.8 mmol/L	> 27.8 mmol/L
Glucose (decreased)	< LLN – 3.0 mmol/L	< 3.0 – 2.2 mmol/L	< 2.2 – 1.7 mmol/L	< 1.7 mmol/L
Creatinine	> ULN – 1.5 × ULN	> 1.5 – 3 × ULN	> 3 – 6 × ULN	> 6 × ULN
Creatinine clearance	< LLN – 60 mL/min	< 60 – 30 mL/min	< 30 – 15 mL/min	< 15 mL/min
Cholesterol	> ULN – 7.75 mmol/L	> 7.75 – 10.34 mmol/L	> 10.34 – 12.92 mmol/L	> 12.92 mmol/L
Albumin	< LLN – 30 g/L	< 30 – 20 g/L	< 20 g/L	--

11.4.2 Statistical Methods

The baseline value for clinical laboratory tests will be the last non-missing measurement on or before the day of the first dose of study drug. Values on Day 1 must also be before the time of first dose if time is available. The same baseline value will be used for changes to Treatment Period visits and changes to Post-Treatment Period visits.

Visit Values

For each protocol-specified laboratory parameter, values at each visit (baseline and post-baseline, including applicable post-treatment visits) will be summarized with the sample size, mean, standard deviation, minimum, median, and maximum.

Change from Baseline

For each laboratory parameter listed in Section 11.4.1, changes from baseline to each post-baseline visit, including applicable post-treatment visits, will be summarized with the sample size, baseline mean; visit mean; and change from baseline mean, standard deviation, minimum, median, and maximum.

Shift Tables

Individual changes in the laboratory parameters listed in Section 11.4.1 will be tabulated using shift tables. Laboratory data values will be categorized as low, normal, or high based on normal ranges of the laboratory used for each sample. Shift tables from baseline to minimum value and maximum value during the Treatment Period will be created. For each parameter, the shift tables will cross tabulate the frequency of subjects with baseline values below/within the normal range to maximum above the normal range and with baseline values within/above the normal range to minimum below the normal range.

Maximum Toxicity Grade

The laboratory parameters listed in Table 11 will be assigned a toxicity grade of 1, 2, 3, or 4. The number and percentage of subjects with a maximum toxicity grade of 1, 2, 3

or 4 during the Treatment Period will be tabulated. To be counted, the post-baseline value must have a toxicity grade that is more extreme than the toxicity grade corresponding to the baseline value. For each laboratory parameter in Table 11, the summary will also include the number and percentage of subjects with a post-baseline maximum of at least Grade 3. A listing of all relevant laboratory parameters will be provided for each subject who had an increase to Grade 2 or higher for any laboratory variable in Table 11.

Assessment of Hepatic Laboratory Values

The number and percentage of subjects with laboratory values meeting the following criteria during treatment will be summarized:

- Post-nadir (preceding value is lower than the subsequent value)
ALT > 5 × ULN (regardless of grade change);
- Total bilirubin ≥ 2 × ULN and > baseline (i.e., a post-baseline value must be more extreme than the baseline value to be considered);
- Post-nadir ALT > 3 × ULN and total bilirubin > 2 × ULN;
- Post-nadir ALT > 3 × ULN and total bilirubin ≤ 2 × ULN.

Four listings (one for each bullet above) of all hepatic laboratory values including ALT, AST, total, indirect and direct bilirubin, ratio of direct to total bilirubin, and alkaline phosphatase values will be provided for each subject who met the criterion defined above.

Hepatic Laboratory Abnormalities of Interest

Among the events assessed under "Assessment of Hepatic Laboratory Values," the following criteria are of interest:

- Confirmed post-nadir ALT > 5 × ULN;
- Post-nadir ALT > 3 × ULN and a concurrent total bilirubin > 2 × ULN with a direct/total bilirubin ratio > 0.4.

To support the assessment of hepatic laboratory abnormalities of interest, the following potential events will be summarized:

- Confirmed post-nadir $ALT > 5 \times ULN$;
- Post-nadir $ALT > 3 \times ULN$ and total bilirubin $> 2 \times ULN$ and direct/total bilirubin ratio > 0.4 .

Two listings (one for each bullet) of all hepatic laboratory values including ALT, AST, total, indirect and direct bilirubin, ratio of direct to total bilirubin, and alkaline phosphatase values will be provided for each subject who met the criterion defined above.

For the **assessments of hepatic laboratory values** and **hepatic laboratory abnormalities of potential interest**, the maximum ratio relative to the ULN will be used to determine if subjects meet any of the criteria listed above. The ALT and total bilirubin values do not need to be concurrent in order to meet the defined criteria in statistical summaries. For ALT, the post-baseline value must represent an increase from the first nadir (including baseline) to be counted. First nadir is defined as the last value prior to the first increase. For total bilirubin, a subject will be counted if the post-baseline laboratory value meets the above criteria regardless of the baseline laboratory value (i.e., the post-baseline laboratory value does not need to be worse than the baseline laboratory value), except where noted above. A confirmed post-nadir increase in ALT is defined as two consecutive values of $ALT > 5 \times ULN$ after nadir, either both during treatment or at the final treatment measurement and the next consecutive post-treatment measurement. A single post-nadir ALT value of greater than $5 \times ULN$ followed by lost to follow-up (no additional ALT values) also will be considered (i.e., will not require confirmation). The ratio of direct to total bilirubin will be calculated using the same date/time sample corresponding to the total bilirubin elevation.

